### **2.3.2 Primary Safety Endpoint Hypothesis**

For the primary safety endpoint, the following hypothesis set will be tested:

$$H_0: p_c - p_p \geq 0.20$$

$$H_a: p_c - p_p < 0.20$$

where  $p_c$  and  $p_p$  are the proportions of subjects in the CAP-1002 and placebo treatment groups, respectively, who experienced the primary safety endpoint.  $H_0$  will be rejected if the upper limit of the 90% confidence interval (CI) for  $p_c - p_p$  is less than 0.20.

### **2.3.3 Secondary Safety Endpoints**

The following adjudicated (see [Section 12](#)) events will be evaluated as secondary safety endpoints over the twelve-month follow-up period:

1. Acute myocarditis possibly attributable to the IP, diagnosed with consideration of clinical

context, with or without a clinically indicated endomyocardial biopsy. In order to be considered related to the IP, humoral or cellular immune reaction specific to CAP-1002 must also be documented for subjects treated with CAP-1002, or a temporal relationship with IP administration must exist for subjects administered placebo. See [Section 12](#) for further information related to blinded adjudication by the CEC.

2. Death due to ventricular tachycardia or ventricular fibrillation defined as occurring with prior ECG documentation of these arrhythmias during ambulatory ECG monitoring in an outpatient setting or during routine ECG monitoring while hospitalized.
3. Sudden unexpected death defined as occurring within one hour of symptom onset, or un-witnessed death in a person previously observed to be well within the preceding 24 hours without an identified cause.
4. MACE, as defined above.
5. New cardiac tumor formation on magnetic resonance imaging (MRI).
6. Any hospitalization due to a cardiovascular (CV) cause or related to IP infusion.
7. Any inter-current CV illness, or one related to IP infusion, which prolongs hospitalization. Evidence of myocardial injury will be assessed by a rule out MI cardiac enzyme protocol performed following IP administration. Troponin and CK-MB will be obtained approximately every 8 hours for the first 24 hours after infusion.
8. New TIMI flow  $\leq 1$  following IP infusion.
9. Development of, or an increase in the frequency of, ventricular tachycardia with a duration of 30 beats or longer ascertained by periodic, protocol-mandated 24 hour ambulatory ECG monitoring.
10. Development of increased anti HLA antibody levels with development of sensitization to HLA antigens specific to the CAP-1002 CDC donor. Elevation of donor-specific antibodies (DSA), using the LABScreen® single-antigen in vitro diagnostic assay that is a Luminex® based antibody detection assay designed to detect Class I or Class II HLA antibodies in human serum or plasma, is defined as mean fluorescence intensity (MFI) above a threshold of 5000; a threshold of 1000 MFI will also be used to evaluate elevation of DSA. See [Section 12](#) for further information related to blinded adjudication by the CEC and [Section 10.2](#) for details related to comparison to placebo.

### **2.3.4 Primary Efficacy Endpoint**

The primary efficacy endpoint is the percent change from baseline in MRI assessment of infarct size as a percent of LV mass 12 months after IP administration.

### 2.3.5 Primary Efficacy Hypothesis

The primary efficacy hypothesis is that CAP-1002 is superior to placebo in reducing infarct size in either all subjects combined (“full group”) or in subjects with recent MI (“subgroup”). A closed testing procedure will be used so that strong control of type 1 error is maintained. Specifically, the following hypothesis sets will be tested:

$$1) \quad H_{0,s}: \mu_{c,s} - \mu_{p,s} = 0 \quad \text{or} \quad H_{0,f}: \mu_{c,f} - \mu_{p,f} = 0 \\ H_{a,s}: \mu_{c,s} - \mu_{p,s} < 0 \quad H_{a,f}: \mu_{c,f} - \mu_{p,f} < 0$$

and

$$2) \quad H_{0,s} \cap H_{0,f}: \mu_{c,s} - \mu_{p,s} = 0 \text{ and } \mu_{c,f} - \mu_{p,f} = 0 \\ H_{a,s} \cap H_{a,f}: \mu_{c,s} - \mu_{p,s} < 0 \text{ or } \mu_{c,f} - \mu_{p,f} < 0$$

where  $s$  denotes the subgroup,  $f$  denotes the full group,  $\mu_{c,s}$  and  $\mu_{p,s}$  are mean percent changes in the CAP-1002 and placebo treatment groups, respectively, in the subgroup, and  $\mu_{c,f}$  and  $\mu_{p,f}$  are mean percent changes in the CAP-1002 and placebo treatment groups, respectively, in the full group.

Therefore, both the intersection null hypothesis ( $H_{0,s} \cap H_{0,f}$ ) and either of the individual null hypotheses ( $H_{0,s}$  or  $H_{0,f}$ ) must be rejected at the (one-sided) 0.025 significance level for the trial to be declared a success. In other words, the null hypothesis of “no treatment effect in the full group and no treatment effect in the recent MI subgroup” must be rejected at the one-side 0.025 significance level, necessarily meaning that either the result is significant in the full group, in the recent MI subgroup, or both. The results of the tests of the individual hypotheses (also at the one-sided 0.025 significance level) determines which specific comparisons are significant.

### 2.3.6 Secondary Efficacy Endpoints

The following secondary efficacy endpoints will be evaluated at 6 and 12 months post IP administration unless otherwise noted:

1. Absolute and relative change from baseline in global LV function measures:
  - a) MRI assessment of LV ejection fraction (LVEF)
  - b) MRI assessment of LV end diastolic volume (LVEDV) and end systolic volume (LVESV) indexed to body surface area (BSA)
2. Absolute and relative change from baseline in structural measures:
  - a) MRI assessment of infarct size as a percent of LV mass
  - b) MRI assessment of infarct size expressed in grams
  - c) MRI assessment of viable mass expressed in grams
  - d) MRI assessment of scar transmurality
3. Absolute and relative change from baseline in regional measures:

- a) MRI assessment of function and structure by segment or groups of segments (e.g., region which received the IP)
- 4. Absolute change from baseline in clinical function/status measures:
  - a) Distance covered in six minute walk test (6MWT)
  - b) Minnesota Living with Heart Failure Questionnaire (MLHFQ) score
  - c) Patient Global Assessment (PGA) score
- 5. Absolute and relative change from baseline in cardiac biomarkers:
  - a) NT-proBNP

### **3. STUDY DESIGN AND SCHEDULE OF EVENTS**

This is a randomized, double-blind, placebo-controlled phase 2 trial designed to evaluate the safety and efficacy of intracoronary delivery of CAP-1002 in subjects with ischemic LV dysfunction and a previous MI. Detailed inclusion and exclusion criteria are in Section 4 of the protocol.

Approximately 120 subjects with a previous anterior MI and resultant ischemic LV dysfunction who meet all inclusion and exclusion criteria will be enrolled into one of two cohorts: the Primary Randomized Cohort and the Exploratory Randomized Cohort. The Primary Randomized Cohort will include approximately 103 subjects who meet compatibility to receive IP from one or more donor(s). Compatibility is achieved when a subject is found at screening to have no pre-existing antibodies against a donor's HLA antigens (i.e., no DSA). The remaining subjects (approximately 17) who have pre-existing antibodies against all available donors will be enrolled in the Exploratory Randomized Cohort so that potential differences in safety and efficacy can be assessed. Each of the two cohorts will be randomized separately. Subjects will be randomized within strata defined by time since MI ("recent" or "chronic") to receive CAP-1002 or placebo in a 2:1 ratio favoring CAP-1002. "Recent" will be defined as more than 4 weeks but within 90 days prior to randomization and "chronic" will be defined as more than 90 days but less than 12 months prior to randomization. Enrollment in the study will end when approximately 130 subjects have been randomized.

Subjects will undergo protocol assessments through 12 months post infusion. Reviews by a Data Safety Monitoring Board (DSMB) will be done per charter at least semi-annually. The DSMB will review both safety and efficacy data after all subjects complete 6 months of follow-up or withdraw from the study. In addition, there will be one administrative interim efficacy analysis after Month 6 MRI measurements are available for all subjects. An additional administrative efficacy analyses may be done on an as-needed basis. Subjects will be followed annually for 5 years post infusion or reference date.

The Schedule of Events is shown in [Appendix A](#).

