2.2 Primary Efficacy Objective

The primary efficacy objective is to evaluate whether administration of CAP-1002 by intracoronary infusion may result in structural cardiac benefits for subjects with ischemic left ventricular dysfunction and a previous MI as measured by infarct size expressed as a percent of left ventricular mass 12 months after infusion; specifically, to test the hypothesis that CAP-1002 is superior to placebo in reducing infarct size, expressed as a percent of left ventricular mass, 12 months after infusion, either in all subjects combined or in subjects with recent MI (≤ 90 days before infusion).

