4.2 Inclusion Criteria

Subjects meeting the following inclusion criteria may be considered for enrollment:

Inclusion Criteria

1. History of MI (STEMI or NSTEMI) within the prior 12 months due to a coronary artery event and evidenced by at least two of the following: typical ischemic symptoms, serial ST-T changes (new ST elevation or new left bundle block) and/or elevated troponin or CK-MB >5 times the upper limit of normal. Also at least one of the following: development of pathological Q wave ECG changes, imaging evidence of new loss of viable myocardium, or new regional wall motion abnormalities.
 - The following assessments will be permitted within 28 days immediately following the subject's MI: signing ICF, review of medical history, review of concomitant medications, and collection of laboratory samples required for assessment of study eligibility criteria (e.g., eGFR, HbA1c, hepatitis serology, HIV serology, LFTs, hematocrit, WBC, and platelet count). All other screening tests, including the subject's cardiac MRI and CT (chest, abdomen, pelvis), must be conducted greater than 28 days post-MI. Infusion must occur within 28 days of the first screening procedure that is performed greater than 28 days post-MI. Relevant safety laboratory sample collections (e.g., chemistry, hematology, urinalysis) may need to be repeated as they must be obtained within 28 days of the subject's infusion.
2. History of percutaneous coronary intervention (PCI), with stent placement resulting in TIMI flow = 3, in the coronary artery supplying the infarcted, dysfunctional territory and through which the treatment will be infused.
3. At least one assessment of left ventricular ejection function (LVEF) ≤ 0.45 as determined by any one of the standard modalities (echocardiography, ventriculography, nuclear imaging, CT and/or MRI) prior to or during the screening period.
 - For subjects that fulfill the criteria of Recent MI (i.e., within 90 days of MI) at time of screening visit: assessment must be post-reperfusion after index MI and the most

recent test prior to or during the screening period.

- For subjects that fulfill the criteria of Chronic MI (i.e., greater than 90 days from MI) at the time of screening visit: assessment must be at least 21 days post-reperfusion after index MI and the most recent test prior to or during the screening period.

Note: subjects may screen as a Recent MI but be randomized into the Chronic MI strata if the infusion date is > 90 days post-MI.

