## 2. STUDY OBJECTIVES, TREATMENTS, AND ENDPOINTS

### 2.1 Objectives

#### 2.1.1 Primary Objectives

The primary safety objective is to test the null hypothesis that the incidence rate of the primary safety endpoint (a composite of peri-procedural clinical events) differs by no more than 0.20 between treatment groups in subjects with ischemic left ventricular (LV) dysfunction and a previous MI receiving CAP-1002 or placebo by intracoronary infusion.

The primary efficacy objective is to test the hypothesis that, in subjects with ischemic LV dysfunction and a previous MI, CAP-1002 by intracoronary infusion is superior to placebo in reducing infarct size, expressed as a percent of LV mass, 12 months after infusion, either in all subjects combined or in subjects with recent MI (<= 90 days before infusion).

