## 7.4 Subgroups

- All TFLs will display data by recent vs. chronic MI. For most analyses, including analysis of the primary efficacy endpoint, subjects randomized in the wrong stratum will be analyzed according to time since the index MI, calculated as:

$$\text{time\_since} = \text{infusion date} - \text{index MI date} + 1$$

If `time_since` is  $\leq 90$  days, the subject will be classified as “recent MI”; otherwise, as “chronic MI.” For the analysis of the primary efficacy endpoint based on the per protocol population, a sensitivity analyses will be done to evaluate the effect of excluding subjects randomized in the wrong stratum from the per protocol population and the effect of analyzing subjects according to the strata in which they were randomized.

- Differences in safety and/or efficacy by subgroups defined by the following classifiers may be explored as part of the final analysis:
  - Demographics (age dichotomized by median, sex, race)
  - Baseline DSA mean fluorescence intensities  $< 500$  vs.  $500-1000$  and/or DSA quartiles
  - Donor, stromal cell derived factor 1 (SDF1) level of lot received, master cell bank, and/or other identified measures of potential cell potency
  - CAP-1002 manufactured with a modified process (“P5”)
  - With vs. without biventricular pacing initiated less than three months before the screening MRI or after the start of the study, the rationale being that this may confound functional and physiologic outcomes in patients with ischemic cardiomyopathy, and it can take up to 3 months post-implant for any effect to occur.
  - Baseline infarct size ( $\leq 20\%$  vs.  $> 20\%$  of LV mass)
  - Baseline LVEF (dichotomized by median)
  - Baseline weight (dichotomized by median)

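### Recent MI, a subgroup that carries a primary hypothesis, is dated to randomisation in SAP 3 and cut one day short in SAP 7.4; both should match the objective (minor, wrong as written)

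*SAP*

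**What the plan says.** The primary efficacy hypothesis may be met in the full group or in the Recent MI subgroup (Protocol 9.5.2; SAP 2.3.5), so success can be declared on Recent MI alone. The documents define that subgroup in several places:

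- **Objective.** Protocol 2.2 tests superiority "either in all subjects combined or in subjects with recent MI (≤ 90 days before infusion". SAP 2.1.1 says the same: "either in all subjects combined or in subjects with recent MI (<= 90 days before infusion".
- **Stratum note.** Under Protocol 4.2, a subject who screens as Recent may "be randomized into the Chronic MI strata if the infusion date is > 90 days post-MI". The randomisation stratum therefore follows the infusion date.
- **Stratum definition in the SAP.** In SAP 3, Recent "will be defined as more than 4 weeks but within 90 days prior to randomization".
- **Analysis rule.** SAP 7.4 covers most analyses, the primary endpoint included: "subjects randomized in the wrong stratum will be analyzed according to time since the index MI, calculated as". The formula is infusion date minus index MI date plus 1. A result of 90 or less is Recent and anything else is Chronic.
- **Sensitivity analysis.** SAP 7.4 also provides: "For the analysis of the primary efficacy endpoint based on the per protocol population, a sensitivity analyses will be done". It examines excluding subjects in the wrong stratum and analysing subjects by the stratum in which they were randomised. The primary analysis itself uses the mITT population (SAP 9).

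Protocol 7.1 asks sites to randomise three or more working days ahead of the infusion, so the two reference dates normally differ. SAP 14 lists no deviations from the protocol's statistical methods.

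**The concern.** A population on which the trial can succeed should have one reference date and one way of counting days. Here the hypothesis and its analysis rule disagree at exactly 90 days, and the SAP's stratum definition uses a different reference date from the protocol's.

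The second conflict affects the wording of the analysis rule. SAP 7.4 is written for subjects randomised in the wrong stratum, and who they are depends on which definition is right. A subject stratified as Recent in accordance with SAP 3 can be in the wrong stratum under the protocol note. The same label drives exclusions in the per protocol sensitivity analysis (SAP 6).

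The stake is that the subgroup tested should be the subgroup named in the objective, under a rule that leaves no discretion. It matters at this boundary because the planning assumptions halve the Month 12 effect across it, from 14.70 to 7.35 (SAP 4, Table 1).

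**Working it through.** **1. The plan's own figure.** SAP 4 claims more than 90% power with 100 subjects. Inputs are Month 12 effects of 14.70 (Recent), 7.35 (Chronic) and 0 (placebo), SD 10, 2:1 allocation and one-sided 0.025; equal strata are assumed.

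- Full group: mean effect (14.70 + 7.35)/2 = 11.025; SE = 10 × √(1/66.7 + 1/33.3) = 2.12; 11.025/2.12 − 1.96 = 3.24, so power is about 99.9%.
- Recent subgroup of 50: SE = 10 × √(1/33.3 + 1/16.7) = 3.0; 14.70/3.0 − 1.96 = 2.94, so power is about 99.8%.
- Simulation of the closed test (8,000 runs, two-sample t-tests at Month 12 in place of the mixed model): 99.9%.

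The stated figure is consistent with these results.

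**2. The definitions side by side.** Let L be the days from randomisation to infusion.

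| Days elapsed, MI to infusion | SAP 3 | Objective and protocol note | SAP 7.4 formula |
|---|---|---|---|
| 89 or fewer | Recent | Recent | Recent |
| 90 | Recent | Recent | Chronic (90 + 1 = 91) |
| 91 to 90 + L | Recent | Chronic | Chronic |
| more than 90 + L | Chronic | Chronic | Chronic |

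Example: randomised on day 88 and infused on day 92. SAP 3 gives Recent. The objective, the protocol note and SAP 7.4 (92 + 1 = 93) give Chronic.

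**3. How many subjects.** The documents give no distribution of time since MI or of L, so these counts rest on assumptions. Protocol 9.2 plans 51–52 Recent subjects. Take 51, spread evenly over days 29 to 90 (62 days).

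- The plus one alone: 51/62 = 0.8 subject.
- The reference date alone: 51 × 3/62 = 2.5 at L = 3, and 51 × 7/62 = 5.8 at L = 7. That is 5% to 11% of 51.
- Both together, SAP 3 against the SAP 7.4 formula: 51 × 4/62 = 3.3 to 51 × 8/62 = 6.6.

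A sparser assumption gives less. Put 51.5 Recent subjects evenly over days 29–90 and 51.5 Chronic subjects evenly over days 91–365 (275 days), by infusion date. The combined count is then 51.5/62 + 51.5 × 3/275 = 1.4 at L = 3, and 51.5/62 + 51.5 × 7/275 = 2.1 at L = 7.

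**4. Effect on power.** Moving 8 Chronic subjects into the Recent subgroup, more than any count in step 3, leaves simulated power at 99.9%. With the assumed effects halved, power is 75.2% with the move and 75.7% without. That difference is within simulation error, since the standard error of each figure is about √(0.75 × 0.25/8,000) = 0.5 points.

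**The case against.** The strongest reply is that the primary analysis is already settled. SAP 7.4 names one formula and one limit for the primary endpoint and dates it to infusion, as the objective does. SAP 3 describes strata for randomisation, and SAP 7.4 anticipates that randomised and analysed strata may differ. On that reading the 2.5 to 5.8 subjects are a randomised-versus-analysed discordance, and only the plus one changes the tested subgroup. This largely stands. It is not complete, because SAP 7.4 is worded for subjects randomised in the wrong stratum. If SAP 3 is the standard, the subject infused on day 92 was stratified correctly, and a literal reader could leave that subject in Recent. The natural reading classifies everyone by the formula, but the text should say so.

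It can also be said that the objective states no counting convention, and that SAP 8.9 counts follow-up inclusively. SAP 7.7, however, counts study day without the plus one, and the protocol note sends a subject to Chronic only beyond 90 days. Day 90 therefore needs one answer.

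A reader might infer more than the documents support:

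- *Three competing analysis definitions, or a third reference date.* SAP 7.4 is dated to infusion; it only counts the MI day as day 1.
- *Erosion of the 2:1 balance, or bias.* Investigators and subjects are blinded, and classification uses the MI and infusion dates. Moving a few subjects adds only chance imbalance, and the full-group test keeps every subject.
- *The IWRS must be changed.* The SAP is version 1.0 of March 2017 and describes Phase 2 as already begun. Nothing shows that SAP 3 was the operating rule, and the protocol already ties the stratum to the infusion date.

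Finally, SAP 9 permits secondary analyses in other populations, so an as-randomised analysis in mITT is possible. It is not committed to.

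**Conclusion.** Wrong as written, and minor. The direct conflict with the hypothesis is the plus one in SAP 7.4, which makes the cut-off 89 elapsed days. Under one subject is expected to be affected: about 0.8, if 51 Recent subjects are spread evenly over days 29 to 90.

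The conflict between SAP 3 and Protocol 4.2 leaves wrong stratum ambiguous. On the same even spread and a 3 to 7 day lag, the reference date could give about 2.5 to 5.8 subjects a randomised stratum different from their analysed one; the sparser assumption gives fewer. The sensitivity analysis that would show the effect of this is planned only in the per protocol population, while the decisive analysis is mITT.

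No loss of power, bias or type I error inflation is shown. The case for correcting the text is that it misstates the membership of a population on which success can be declared.

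**What to change.** 1. In SAP 7.4, compute days since MI as infusion date minus index MI date, without the plus one. Classify every infused subject as Recent at 90 or fewer and Chronic otherwise. The mITT population contains only infused subjects, so this covers the primary analysis.
2. In SAP 3, change the reference date for the strata from randomisation to infusion, to agree with Protocol 4.2.
3. Define wrong stratum in SAP 6 and 7.4 as disagreement between the randomised stratum and the rule in item 1.
4. Document which date the IWRS actually used to assign strata. Do not alter a live randomisation system for this.
5. Run the as-randomised-stratum sensitivity analysis of the primary endpoint in the primary mITT population as well as per protocol.

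The cost is SAP wording, a short note on IWRS practice, and one extra sensitivity run.

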## 4. SAMPLE SIZE AND POWER CALCULATIONS

Power calculations were done using Monte Carlo simulation based on observed data from two previous clinical trials in which subjects similar to those being enrolled in ALLSTAR Phase 2, i.e., with ischemic LV dysfunction, were treated with CDCs by intracoronary infusion: CADUCEUS, a phase 1 randomized, controlled trial, and ALLSTAR Phase 1, the open-label safety phase of the current trial. ALLSTAR Phase 1 was used for the assumed means and SDs and CADUCEUS was used for the treatment effect in Chronic MI patients relative to Recent MI. A simulation of the closed testing procedure to test the primary efficacy endpoint at the final analysis using parameters shown in [Table 1](#) was done (see [Section 2.3.5](#)).

**Table 1. Assumed Mean and Standard Deviation (SD) Percent Reduction in Scar Size at Months 6 and 12.**

	Month 6		Month 12	
	Mean	SD	Mean	SD
CAP-1002 Recent	6.20	10.00	14.70	10.00
CAP-1002 Chronic	3.10	10.00	7.35	10.00
Placebo	0.00	10.00	0.00	10.00

The simulation results indicated that, under these assumptions, the trial will have more than 90% power to be declared successful with a total sample size of 100.

